#### **9.4.2 Non-Serious Adverse Events**

The recording of non-serious AEs will begin after the patient signs the informed consent form and will stop at the end of the patient's follow-up period, which is defined as the Week 65 visit for patients not continuing with the OLE and going straight to the Post-Treatment Follow-up period or the Week 117 visit for patients who continue with the OLE. The Investigator will monitor each patient closely and record all observed or volunteered AEs on the Adverse Event Case Report Form.

#### **9.4.3 Evaluation of Adverse Events (Serious and Non-Serious)**

The Investigator's opinion of the following should be documented on the Adverse Event Case Report Form:

##### **9.4.3.1 Relationship to the Study Drug**

The event's relationship to the Study Drug is characterized by 1 of the following:

- **Related:** There is clear evidence that the event is related to the use of Study Drug, e.g., confirmation by positive re-challenge test
- **Possible:** The event cannot be explained by the patient's medical condition, concomitant therapy, or other causes, and there is a plausible temporal relationship between the event and Study Drug administration
- **Unlikely/Remote:** An event for which an alternative explanation is more likely (e.g., concomitant medications or ongoing medical conditions) or the temporal relationship to Study Drug administration and/or exposure suggests that a causal relationship is unlikely (For reporting purposes, Unlikely/Remote will be grouped together with Not Related)
- **Not Related:** The event can be readily explained by the patient's underlying medical condition, concomitant therapy, or other causes, and therefore, the Investigator believes no relationship exists between the event and Study Drug

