#### 9.3.2 *Adverse Reaction and Suspected Adverse Reaction*

An adverse reaction is any AE caused by the Study Drug.

A suspected adverse reaction is any AE for which there is a reasonable possibility that the drug caused the AE. A suspected adverse reaction implies a lesser degree of certainty about causality than an adverse reaction.

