- TEAEs potentially related to Study Drug. Related is defined as “Related”, “Possible”, or missing relationship to Study Drug
- Any treatment-emergent adverse event by severity. At each level of patient summarization, a patient with multiple events is counted only once according to the worst reported severity. Adverse events with missing severity will be categorized as “Missing” for this summary.
- TEAEs potentially related to Study Drug by severity
- Serious TEAEs
- Serious TEAEs potentially related to Study Drug
- TEAEs leading to permanent treatment discontinuation
- TEAEs leading to death.

Adverse event summaries will be presented by descending frequency of the percentage of patients in the Total column. An overview of AEs will be provided for all TEAEs. Treatment-emergent AEs, treatment-emergent SAEs, TEAEs that lead to treatment discontinuation, and TEAEs leading to death will be listed. Note that imputed dates will be used for defining TEAEs and classification of TEAEs into analysis periods. Originally reported dates will be used for listings.

For AEs occurred during Randomized Treatment Post-Treatment Period, the frequency of patients and number of events of any TEAEs, Serious TEAE will be summarized by MedDRA preferred term and system organ class.

In addition, an overview of adjudicated AEs will be provided for pancreatitis and MACE separately. Adjudicated events will also be listed.

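### The definition of 'Possible' relatedness is stricter than the protocol's own suspected-reaction definition and leaves a gap in the causality scale that can keep events out of the investigator-based related-AE tables

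*Protocol*

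**What the plan says.** Protocol 9.3.2 sets the standard: "A suspected adverse reaction is any AE for which there is a reasonable possibility that the drug caused the AE". It adds that this implies less certainty than an adverse reaction proper.

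Protocol 9.4.3.1 then gives the investigator four choices:

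- **Related:** the evidence for a drug cause must be clear, for instance from a positive rechallenge.
- **Possible:** "The event cannot be explained by the patient's medical condition, concomitant therapy, or other causes, and there is a plausible temporal relationship" to Study Drug administration.
- **Unlikely/Remote:** "An event for which an alternative explanation is more likely", or timing or exposure that makes a causal link unlikely. The section adds: "For reporting purposes, Unlikely/Remote will be grouped together with Not Related".
- **Not Related:** another cause readily accounts for what happened, so the investigator sees no relationship.

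SAP 3.7.2 builds the potentially related tables, for all TEAEs and for serious TEAEs, from these ratings: "Related is defined as “Related”, “Possible”, or missing relationship to Study Drug". SAP Appendix A lists treatment-emergent related AEs as a separate listing and table for the DSMB.

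**The concern.** The two protocol sections apply different tests. Under 9.3.2 a competing cause does not rule out a suspected reaction. Under 9.4.3.1, read literally, a competing cause that could explain the event rules out 'Possible', and 'Related' demands clear evidence. An event can therefore meet the protocol's definition of a suspected reaction and still be barred from both categories that the SAP counts as related.

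This is not a remote case here. Inclusion criteria 4 to 6 in Protocol 5.1 require treated type 2 diabetes, raised triglycerides and fatty liver, so competing explanations will be common.

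- **Hypoglycemia:** background anti-diabetic therapy is one candidate cause. Study drug is another, since Protocol 2.3.4 reports a 57% improvement in insulin sensitivity on it.
- **Transaminase rises:** Protocol 2.1 describes these as common in the disease itself.
- **Bleeding:** exclusion 17i allows stable oral anticoagulants, while Protocol 2.3.4 describes platelet falls that led to Study Drug being interrupted or stopped.

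At stake is whether the related-AE tables and the DSMB's related-AE output mean what their titles say. This matters most in the open-label extension, where every patient receives volanesorsen and there is no concurrent placebo group to help judge causality.

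**Working it through.** No arithmetic applies to the definitions, so the check is to take each type of event through the four categories and then through the SAP rule.

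| Type of event | Category as worded | Counted as related in SAP 3.7.2? |
|---|---|---|
| Clear evidence of a drug cause | Related | Yes |
| No other cause can explain it; timing plausible | Possible | Yes |
| Another cause is more likely, or the timing argues against the drug | Unlikely/Remote | No |
| Another cause readily explains it; no relationship believed | Not Related | No |
| Another cause could explain it but is equally or less likely than the drug; timing plausible; no clear evidence | None | Not determined |
| Relationship left blank | Missing | Yes |

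The fifth row is the defect. Taking that event through each category in turn:

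1. It is not 'Related', because there is no clear evidence.
2. It is not 'Possible', because another cause could explain it.
3. It is not 'Unlikely/Remote', because the alternative is not the more likely one and the timing is plausible.
4. It is not 'Not Related', because the investigator does not believe a relationship is absent.

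It can nonetheless satisfy 9.3.2. Two credible causes, neither favoured over the drug, are compatible with a reasonable possibility that the drug is responsible.

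The scale still requires one answer. If the investigator relaxes 'Possible', or leaves the field blank, the event is counted. If the investigator holds to the literal wording of 'Possible' and must still choose, the remaining categories are ones that the SAP leaves out. The documents do not say which will happen.

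Write N for the number of such events that meet 9.3.2 and p for the share rated downward. The under-count against 9.3.2 is then p × N. It runs from 0 (p = 0) to N (p = 1), and the documents give neither quantity.

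**The case against.** The strongest reply is that little depends on this category, and much of that reply stands.

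- **Expedited reporting.** A reader might infer that events with a competing cause drop out of suspected-reaction reporting. For serious events the documents do not support this. Protocol 9.4.1 sends every SAE to the Sponsor whatever its causality rating. Protocol 9.2 then requires an independent Sponsor assessment of relatedness, which may upgrade the investigator's opinion and may not downgrade it for the SUSAR decision. No such step is described for non-serious AEs or for the SAP tables.
- **Other safety analyses.** All TEAEs, serious TEAEs, TEAEs leading to discontinuation and deaths are tabulated without regard to causality (SAP 3.7.2). Injection-site and flu-like reactions are defined by term and timing. AEs of special interest are defined by MedDRA queries or terms (SAP 3.7.2.1 to 3.7.2.3). Liver enzymes and platelets have threshold and shift tables (SAP 3.7.4). Pancreatitis and MACE are adjudicated blind (Protocol 9.4.4). No event is lost from the safety analysis as a whole.
- **No downward default.** A reader might infer that every event with a competing cause is pushed into 'Unlikely/Remote'. No text says so, and that category has its own test, which these events also fail. Leaving out events whose alternative is more likely is no contradiction of 9.3.2.
- **Population and event are different things.** A reader might infer from the entry criteria that 'Possible' is out of reach for whole classes of event. The test is whether the condition explains the particular event, not whether the patient has the condition.

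The reply does not remove the inconsistency between 9.3.2 and 9.4.3.1, the missing category, or the direct use of the ratings in the related-AE tables.

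**Conclusion.** The point holds as a defect of definition with a limited reach. 'Possible' is worded more strictly than 9.3.2, and the four categories omit events with plausible timing and an alternative no more likely than the drug. Applied literally, the wording can keep such events out of the potentially related TEAE and serious-TEAE tables and out of the DSMB related-AE output.

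Two assumptions underlie this. The first is that at least some investigators apply 'Possible' as written; the CRF guidance is not among the documents and may already soften it. The second is that the DSMB output uses the same investigator rating, since SAP Appendix A does not define related.

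The size cannot be estimated. Assuming a share of events with a competing cause and reading it off as the percentage under-count would only return the assumption. The conclusion that drug-related harm is under-counted in the trial overall is not supported. The point is worth correcting, but it does not undermine the comparisons of all TEAEs, laboratory results or adjudicated events.

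**What to change.** In Protocol 9.4.3.1, redefine 'Possible' along these lines: there is a reasonable possibility that Study Drug caused the event and the timing is plausible, even if another cause could also explain it. Keep 'Unlikely/Remote' for events where an alternative is more likely or the timing makes a causal link unlikely. Events in the fifth row of the table then fall under 'Possible', and the scale agrees with 9.3.2. Put the same wording in the CRF guidance. The SAP counting rule can stay as it is.

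Rewording does not change ratings already given, and SAP 3.1 and 3.8 say that treatment was discontinued before the planned period was completed. Where causality has already been recorded under the present definition, state beside the related-AE tables that 'Possible' required the absence of another explanation, so the counts may omit events with a credible competing cause.

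The cost is a wording change in the protocol and CRF guidance, plus a note in the study report. Re-rating past events would need the investigators to reassess them and is not part of this proposal. The downside is that somewhat more events will be rated possibly related. No dose, stopping rule or efficacy analysis is touched.

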##### **9.4.3.2 Severity**

The event's severity is characterized by 1 of the following:

- **Mild:** The event is easily tolerated by the patient and does not affect the patient's usual daily activities
- **Moderate:** The event causes the patient more discomfort and interrupts the patient's usual daily activities
- **Severe:** The event is incapacitating and causes considerable interference with the patient's usual daily activities

If the event is an SAE, then all applicable seriousness criteria must be indicated (criteria listed in Section 9.3.3).

#### **9.4.3.3      *Action Taken with Study Drug***

Action taken with Study Drug due to the event is characterized by 1 of the following.

- **None:** No changes were made to Study Drug administration and dose
- **Permanently Discontinued:** Study Drug was discontinued and not restarted
- **Temporarily Interrupted, Restarted – Same Dose:** Dosing was temporarily interrupted or delayed due to the AE and restarted at the same dose
- **Reduced Schedule:** Dosing frequency was reduced

#### **9.4.3.4      *Treatment Given for Adverse Event***

Any treatment (e.g., medications or procedures) given for the AE should be recorded on the Adverse Event Case Report Form. Treatment should also be recorded on the concomitant treatment or ancillary procedures eCRF, as appropriate.

#### **9.4.3.5      *Outcome of the Adverse Event***

If the event is a non-serious AE, then the event's outcome is characterized by 1 of the following:

- **AE Persists:** Patient terminates from the trial and the AE continues
- **Recovered:** Patient recovered completely from the AE
- **Became Serious:** The event became serious (the date that the event became serious should be recorded as the Resolution Date of that AE and the Onset Date of the corresponding SAE)
- **Change in Severity (if applicable):** AE severity changed

If the event is an SAE, then the event's outcome is characterized by 1 of the following:

- **Ongoing:** SAE continuing
- **Persists (as non-serious AE):** Patient has not fully recovered but the event no longer meets serious criteria and should be captured as an AE on the non-serious AE eCRF (the SAE resolution date should be entered as the date of onset of that AE)
- **Recovered:** Patient recovered completely from the SAE (the date of recovery should be entered as the SAE resolution date)
- **Fatal:** Patient died (the date of death should be entered as the SAE resolution date)

#### **9.4.4      *Adjudication Committees***

All SAEs that occur during the study that are consistent with a major adverse cardiovascular event (MACE) will be adjudicated by a blinded, independent committee as outlined in the MACE Adjudication Charter. In addition, this committee will also adjudicate the data for

episodes of MACE over the last 3 years prior to randomization, collected by review of each patient's medical chart.

All AEs and SAEs that occur during the study that are consistent with an event of acute pancreatitis will be adjudicated by a blinded, independent committee according to the Atlanta classification of acute pancreatitis (Banks et al. 2013) and as outlined in the Pancreatitis Adjudication Charter.

## **9.5 Procedures for Handling Special Situations**

### ***9.5.1 Abnormalities of Laboratory Tests***

Clinically-significant abnormal laboratory test results may, in the opinion of the Investigator, constitute or be associated with an AE. Examples of these include abnormal laboratory results that are associated with symptoms, or require treatment, e.g., bleeding due to thrombocytopenia, tetany due to hypocalcemia, or cardiac arrhythmias due to hyperkalemia. Whenever possible, the underlying diagnosis should be listed in preference to abnormal laboratory values as AEs.

Clinically-significant abnormalities will be monitored by the Investigator until the parameter returns to its baseline value or until agreement is reached between the Investigator and Sponsor Medical Monitor. Laboratory abnormalities deemed not clinically-significant (NCS) by the Investigator should not be reported as AEs. Similarly, laboratory abnormalities reported as AEs by the Investigator should not be deemed NCS on the laboratory sheet.

The Investigator is responsible for reviewing and signing all laboratory reports. The signed clinical laboratory reports will serve as source documents.

### ***9.5.2 Prescheduled or Elective Procedures or Routinely Scheduled Treatments***

A prescheduled or elective procedure or a routinely scheduled treatment will not be considered an SAE, even if the patient is hospitalized; the Study Center must document all of the following:

- The prescheduled or elective procedure or routinely scheduled treatment was scheduled (or was on a waiting list to be scheduled) prior to obtaining the patient's consent to participate in the Study
- The condition that required the prescheduled or elective procedure or routinely scheduled treatment was present before and did not worsen or progress in the opinion of the Investigator between the patient's consent to participate in the Study and the timing of the procedure or treatment
- The prescheduled or elective procedure or routinely scheduled treatment is the sole reason for the intervention or hospital admission

### ***9.5.3 Dosing Errors***

Study Drug errors should be documented as Protocol Deviations. A brief description should be provided in the deviation, including whether the patient was symptomatic (list symptoms) or asymptomatic, and the event accidental or intentional.

Dosing details should be captured on the Dosing Case Report Form. If the patient takes a dose of Study Drug that exceeds protocol specifications and the patient is symptomatic, then the symptom(s) should be documented as an AE and be reported per [Section 9.4](#).

**Should an overdose occur**, the Investigator or designee should refer to the Guidance to Investigator's section of the Investigator's Brochure and contact the Sponsor or designee within 24 hours.

#### **9.5.4     *Contraception and Pregnancy***

Male patients and female patients of childbearing potential must continue to use appropriate contraception with their partners, or refrain from sexual activity, as described in [Section 6.3.1](#).

If a patient becomes pregnant or a pregnancy is suspected, or if a male patient makes or believes that he has made someone pregnant during the study, then the Study Center staff must be informed immediately. An Initial Pregnancy Form should be submitted to the Sponsor or designee **within 24 hours** of first learning of the occurrence of pregnancy. Follow-up information including delivery or termination is reported on Follow-up Pregnancy Forms and reported within 24 hours.

Payment for all aspects of obstetrical care, child or related care will be the patient's responsibility.

**Female patients:** If a suspected pregnancy occurs while on the study (including Follow-up), a pregnancy test will be performed. The patient with a confirmed pregnancy will be immediately withdrawn from treatment with Study Drug. However, the patient will be encouraged to complete the post-treatment follow-up portion of the study to the extent that study procedures do not interfere with the pregnancy. Regardless of continued study participation, the study physician will assist the patient in getting obstetrical care and the progress of the pregnancy will be followed until the outcome of the pregnancy is known (i.e., delivery, elective termination, or spontaneous abortion). If the pregnancy results in the birth of a child, the Study Center and Sponsor may require access to the mother and infant's medical records for an additional 8 weeks after birth.

**Male patients:** The progress of the pregnancy in a male patient's partner should be followed until the outcome of the pregnancy is known (i.e., delivery, elective termination, or spontaneous abortion). If the pregnancy results in the birth of a child, additional follow-up information may be requested for the mother and infant. Follow-up will be performed to the extent permitted by applicable regulations and privacy considerations.

### **10.     STATISTICAL CONSIDERATIONS**

#### **10.1     *Study Endpoints***

For all lipid parameters, the baseline is defined as the average of Day 1 pre-dose assessment and the last fasting measurement prior to Day 1.

The primary analysis time point is at the end of Month 3 where the value at primary analysis time point is defined as the average of Week 12 and Week 13 fasting assessments. The value at

Month 6 is defined as the average of Week 25 and Week 26 and the value at Month 12 is defined as the average of Week 50 and Week 52 fasting assessments.

#### ***10.1.1 Primary Endpoint***

The primary efficacy analysis will be the comparison of percent changes from Baseline to the primary analysis time point in fasting TG between ISIS 304801 300 mg once-weekly group and placebo group in the Full Analysis Set (FAS).

#### 10.1.4 Safety Endpoints

Safety endpoints include the following:

- AEs including adjudicated events of pancreatitis and MACE
  - Vital signs and weight
  - Physical examinations
  - Clinical laboratory tests (serum chemistry, hematology, coagulation, urinalysis)
  - Echocardiography
  - ECGs
  - Use of concomitant medications
  - MRIs

## 10.2 Sample Size Considerations

Based upon prior clinical trial experience with ISIS 304801, it is estimated that the standard deviation (SD) of the percent change in total TG is approximately 40%. With 20 ISIS 304801 300 mg once-weekly patients and 20 placebo patients there would be approximately 80% power

to detect a 40% difference in TG levels between treatment groups at an alpha level of 0.05, assuming 50% reduction in the ISIS 304801 treated patients and 10% reduction in the placebo patients.

A sample size of 35 patients (20 active and 15 control) provides 92% power to detect a liver fat treatment difference of 4.7% based on a between patient standard deviation of 4% and a two-sided alpha of 0.05.

### **10.3 Populations**

Full Analysis Set (FAS): All patients who are randomized and received at least 1 dose of Study Drug and have a Baseline TG assessment. The FAS represents the practically-feasible intent-to-treat (ITT) population as delineated in ICH Guideline E9.

Per Protocol Set (PPS): Subset of the FAS who received 9 of 13 doses and with no significant protocol deviations that would be expected to affect efficacy and PD assessments. The detailed criteria will be specified and finalized prior to the final database lock.

Safety Set: All patients who are randomized and receive at least 1 dose of Study Drug.

PK Population: All patients who are randomized, receive at least 1 dose of active Study Drug (ISIS 304801), and have at least 1 PK sample collected and analyzed.

### **10.4 Definition of Baseline**

The baseline for fasting lipid measurements is defined as the average of Day 1 pre-dose assessment and the last measurement prior to Day 1. The baseline for other measurements is defined as the last non-missing assessment prior to the first dose of Study Drug.

### **10.5 Interim Analysis and Early Stopping Guidelines**

An interim analysis of the study is not planned.

### **10.6 Planned Methods of Analysis**

All eCRF data, lab data transfers, as well as any outcomes derived from the data, will be provided in the patient data listings. Patient data listings will be presented for all patients enrolled into the study. Descriptive summary statistics including n, mean, median, standard deviation, standard error, interquartile range (25th percentile, 75th percentile), and range (minimum, maximum) for continuous variables, and counts and percentages for categorical variables will be used to summarize most data by treatment group. Where appropriate, p-values will be reported. All statistical tests will be conducted using 2-sided tests with 5% Type I error rates unless otherwise stated.

All primary, secondary [REDACTED] endpoints will be assessed in the FAS and PPS, with the former being the basis for the primary efficacy analysis. All safety assessments will be performed on the Safety Set. PK endpoints will be assessed in the PK Set as applicable.

